5.3 Strategies for Recruitment and Retention

Participants will be recruited from direct contact with patients who have relevant diagnoses recorded in electronic health records or patient registries at the Brotman Facial Pain Clinic and from the Clinic of Oral and Maxillofacial Surgery at the University of Maryland, School of Dentistry. Providers at these clinics will be made aware of the study and asked to inform their patients about the study and to provide them with study contact information. Previous study participants who gave prior permission may be contacted. Participants may be also recruited through advertisements, websites, print, and electronic

media. All recruitment materials will be submitted to the IRB for review and approval prior to their use.

Participants will be contacted to be reminded of each upcoming visit by telephone, text message, email, or letter. Participants will be informed about the importance of keeping each scheduled appointment, and they will be instructed to contact the study staff as soon as possible in case they are unable to attend a scheduled appointment. Participants who miss a scheduled visit without notifying the study staff will be contacted by telephone, text message, email, or letter to encourage their continued participation in the study and to ask them to contact the study team concerning their next appointment. Unscheduled visits may occur at the investigator's discretion (Section 7.6).

Participants will be compensated for their participation in the study in an amount stated in the informed consent form. In some cases, the participant may be eligible for reimbursement of travel expenses.

5.4 Treatment Assignment Procedures

This will be a conventional factorial design, randomized, double-blinded clinical trial with two parallel arms to evaluate efficacy of Erenumab:

- Erenumab, a monoclonal antibody medication that inhibits the CGRP pathway, which is FDA-approved for the prevention of migraine in adults. The comparison will be to placebo.

5.4.1 *Randomization Procedures (if applicable)*

Extensive screening procedures of potential participants to determine their eligibility based on the inclusion and exclusion criteria will be carried out prior randomization. Participants who do not meet these criteria will not be enrolled in the study.

Randomization visit will be within 7 days after Visit 0, eligibility will be further confirmed based on completion of Daily Symptom Diaries and pain intensity score. Qualified participants will be randomly assigned to one of the two arms of the study in a 1:1 ratio:

- 1) Investigational arm: Erenumab: N= 30 participants
- 2) Placebo: N=30 participants

Randomization

Subjects will be randomized to the investigational treatment group (Erenumab) or the placebo group using a blocked randomization scheme. The examiners and patients will be blind to the group assignment. Randomization will be done by Investigational Drug Services (IDS/Research pharmacy). There will be a 1:1 ratio of treatment to placebo participants.

Blinding

Blinding will be done by Investigational Drug Services (IDS). The PI and study staff will be blind to what the participant is receiving.

Treatment/randomization codes

IDS will be responsible for randomization of participant assignment to either the study medication or placebo groups. IDS will use a random number generation program to determine assignment.

5.4.2 Masking and Unblinding Procedures (if applicable)

All study staff, including investigators, study care providers, study clinician, study coordinators, and research assistants, will remain blinded to the participants' medication assignments throughout the study. Erenumab and Placebo will be packaged in identical vials and stored. Only IDS, the research pharmacy will be unblinded. If the IRB and/or Data and/or the Safety Monitoring Board (DSMB) request an unblinded data report during the data collection period, an unblinded biostatistician will generate the report.

Unmasking/unblinding prior to study completion will occur only if there is evidence that a participant's health or safety is threatened and therefore, knowledge of treatment assignment is necessary to protect the participant.

Except in extreme medical emergencies, before a participant's treatment assignment is revealed, the investigator must confer the request for unmasking with the IDS. For a medical emergency that occurs during business hours, the site investigator will contact the IDS to determine the participant's treatment assignment; for a medical emergency that occurs outside of business hours, medical personnel will contact the IDS pharmacy to determine the treatment assignment.

An event is considered an extreme medical emergency when medical management of a participant requires the knowledge of the treatment assignment. Study participants will be provided with instructions and contact information for emergency situations. Emergency unmasking will be recorded and reported to the PI, and the medical monitor as soon as possible, with a full accounting of the event, date and time of occurrence, the reason for unmasking, and names of all individuals who were notified of the emergency. Unblinding will be reported to the Data Safety Monitoring Board (DSMB) and IRB according to the University of Maryland policies and guidelines.

5.5 Subject Withdrawal

Subjects may withdraw voluntarily from the study or the investigator may terminate a subject's participation at any time.

5.5.1 Reasons for Withdrawal

Participants are free to withdraw from participation in the study at any time, for any reason, with no explanation upon request. This decision will not interfere or alter in any way their following treatments and pain management if they are patients of the dental school, the Brotman Facial Pain Clinic or the Oral and Maxillofacial Surgery Clinic.

If a participant does not return for a scheduled visit, every effort will be made to contact the participant and to document the outcome. If a participant withdraws consent and refuses to come to an Early Termination Visit, no further evaluations will be performed, and no attempts will be made to collect additional data.

Investigators may withdraw a participant for any of the following reasons:

- Withdrawal of consent
- The participant does not meet eligibility criteria for randomization.
- Any clinical adverse event (AE), laboratory abnormality, or other medical condition or situation occurs such that continued participation in the study would not be in the best interest of the participant.
- The subject meets an exclusion criterion (either newly developed or not previously recognized) that precludes further study participation.
- Pregnancy
- At Investigator discretion

5.5.2 Handling of Subject Withdrawals or Subject Discontinuation of Study Intervention

Participants withdrawn after randomization will not be replaced. Participants who are withdrawn voluntarily or by the investigator will be discontinued from the study.

Study staff will complete a study disposition form in the eCRF, indicating the reason for discontinuation.

If the patient is a patient from the school and/or is interested in following TMD care at the Brotman Facial Pain clinic, will be referred to the faculty practice clinic front desk for information and to schedule an appointment if wants to.

Unblinding, if required, will be carried out according to the procedures described in

Section 5.4.2. A participant who has an AE at the time of discontinuation will be followed until the event returns to baseline, resolves, or is stabilized. If the AE does not meet one of these outcomes within 30 days after discontinuation or the end of the study, the participant will be referred to an appropriate provider for continued medical care (See section 9.2).

5.6 Premature Termination or Suspension of Study

This study may be suspended or prematurely terminated if there is sufficient reasonable cause as determined by the sponsor, the PI, medical monitor, DSMB, or IRB. Written notification, documenting the reason for study suspension or termination, will be provided by the suspending, or terminating party. If the study is prematurely terminated or suspended, the principal investigator will promptly inform the IRB and will provide the reason(s) for suspension or termination.

Circumstances that may warrant termination include, but are not limited to:

- Determination of unexpected, significant, or unacceptable risk to subjects.
- Insufficient adherence to protocol requirements.
- Data that are not sufficiently complete and/or evaluable.
- Determination of futility.

6 STUDY INTERVENTION

6.1 Study Product Description

The investigational drug is Erenumab-aooe (Aimovig), an FDA approved medication for the prevention migraine in adults. Erenumab-aooe is a fully human monoclonal antibody IgG2 that binds in a competitive and reversible manner to the Calcitonin Gene Related Peptide (CGRP) receptor with greater selectivity. It is available as a subcutaneous injection only and it is used once a month.

Erenumab injection is a sterile, preservative-free, clear to opalescent, colorless to light yellow solution for subcutaneous administration. The needle shield of the prefilled syringes contain dry natural rubber (a derivative of latex). The syringe is a prefilled glass syringe with a stainless-steel needle and delivers 1 mL of 70 mg/mL. Each 1 mL 70 mg single-dose prefilled glass syringe contains 70 mg erenumab-aooe, acetate (1.5 mg), polysorbate 80 (0.10 mg), and sucrose (73 mg).

The placebo injection is a sterile solution. The syringe is a 1 mL prefilled glass syringe of [REDACTED] Sodium Acetate, [REDACTED] Sucrose, [REDACTED] polysorbate 20, pH 5.2

6.1.1 Acquisition

Our study will use Erenumab at the dosage of 70 mg once monthly. The drug will be acquired from AMGEN, the manufacturer, and shipped to the research pharmacy at the University of Maryland. The research pharmacy will release the drug to study personnel, who will dispense it to the participants at study visits. The placebo will be also acquired from AMGEN and will be packaged, labeled, dispensed, and administered in the same manner as described above for the active drug. Placebo ingredients are [REDACTED] Sodium Acetate [REDACTED] Sucrose, [REDACTED] polysorbate 20, pH 5.2. Storage requirements for the placebo are the same as for the active drug.

6.1.2 Formulation, Packaging, and Labeling

An Erenumab 70 mg/mL, 1 mL prefilled glass syringe (15mM sodium acetate, 8.5% (w/v) sucrose, 0.010% (w/v) polysorbate 80, pH 5.2) will be used. The placebo will be Placebo 1 mL in a prefilled glass syringe consisting of [REDACTED] Sodium Acetate, [REDACTED] Sucrose, [REDACTED] polysorbate 20, pH 5.2. Neither study personnel nor study participants will be able to differentiate the study drug from placebo by appearance alone.

The research pharmacy will label and dispense the autoinjectors in individual cartons. The cartons will be labeled with the following information:

- Name and address of the dispensing pharmacy
- Protocol number
- Name of the drug labeled as “Erenumab or placebo” to protect the blinding
- Strength of the drug or placebo (70mg/ml). Dispense 1
- Name of the prescribing clinician
- Instructions for use
- Participant name and clinic record number
- Date dispensed
- The following statement: “Limited by Federal Law to Investigational Use Only”

6.1.3 *Product Storage and Stability*

Erenumab will be stored following the instructions of the manufacturer. Erenumab needs to be stored refrigerated at 2°C to 8°C (36°F to 46°F) in the original carton to protect from light until time of use.

- If removed from the refrigerator, Erenumab should be kept at room temperature (up to 25°C [77°F]) in the original carton and must be used within 7 days. It will be thrown away if it has been left at room temperature for more than 7 days. It should not be freeze or shaken.

Study personnel will pick up the study product from the research pharmacy the day prior or the same day that will be administered to participants. If picked up a day before to be administered, the study product will be storage in an allocated refrigerator specifically for its storage at the Brotman Facial Pain Clinic.

6.2 Dosage, Preparation and Administration of Study Product

Erenumab 70 mg/mL or placebo prefilled glass syringe will be administered subcutaneously once monthly.

Erenumab or placebo will be administered by the study personnel who will be trained in how to administer it using the single-dose prefilled syringe, including aseptic technique and according to the instructions of the manufacturer.

- Prior to subcutaneous administration, allow Erenumab or placebo to sit at room temperature for at least 30 minutes protected from direct sunlight.
- Do not warm by using a heat source such as hot water or a microwave.
- Do not shake the product.

- Inspect visually for particulate matter and discoloration prior to administration [see Dosage]
- Do not use if the solution is cloudy or discolored or contains flakes or particles.
- Erenumab or placebo will be administered in the abdomen, thigh, or upper arm subcutaneously.
- It will not be injected into areas where the skin is tender, bruised, red, or hard.
- Both prefilled autoinjector and prefilled syringe are single-dose and deliver the entire contents.

Erenumab or placebo administration to participants will be once a month for 3 months on Visits 1-3. The study personnel will explain the participant how it will be injected. Participants will receive the first dose on Visit 1. The second dose a month after on Visit 2 and the third and last dose a month after the second dose on Visit 3 for a total of 3 cycles.

Erenumab or placebo is for subcutaneous use only. The needle shields of erenumab and placebo prefilled syringe contain dry natural rubber (a derivative of latex), which may cause allergic reactions in individuals sensitive to latex. Sensitivity to latex is included in the exclusion criteria (See 5.2)

6.3 Modification of Study Product Administration for a Subject

If a dose of Erenumab is missed, will be administered as soon as possible. Thereafter, Erenumab will be scheduled monthly from the date of the last dose.

The safety profile of erenumab has been favorable in clinical trials and in the post-marketing setting. A limited number of adverse drug reactions (injection site reactions, constipation, muscle spasm, and pruritus) have been identified at low frequencies (< 5%) in clinical trials. In the long-term use of erenumab, the safety profile remained consistent through 5 years of open-label treatment. In post-marketing settings, hypersensitivity reactions (including rash, angioedema and anaphylactoid reactions) and constipation with serious complications have been reported. In addition, oral sores (eg, stomatitis, mouth ulceration, oral mucosal blistering), alopecia and rash (eg, rash papular, exfoliative rash, rash erythematous, urticaria, blister) have been observed in post-marketing surveillance.

Hypertension or worsening of high blood pressure can happen after receiving Erenumab. Hypertension is in our exclusion criteria, however if a new onset of hypertension occurs, the participant will be withdrawn of the study and will be the participant will be referred to an appropriate practitioner for continued care (see section 9.2).

Participants will be closely monitored for any of these AEs, during the clinic visit and between visits by telephone. Potential risks and discomforts will be clearly stated in the ICF. Exclusion criteria includes medical history of constipation or taking medications associated with decrease of G.I motility as well as pre-existent hypertension (See 5.2). If the participant reports a hypersensitivity reaction (rash, angioedema, anaphylaxis), new onset constipation or new onset of hypertension or any of the reactions described above, if there is worsening of TMD signs and symptoms during the 18 weeks of participation or if the participant decides against using Erenumab, he/she will be discontinued from the study (See 2.3.1 and 5.5.2).

The following expected events will not be considered reportable AEs:

- Temporary injection site reactions such as pain, erythema, pruritus after the injection of Erenumab
- Minor bleeding or bruising resulting from the blood draw
- Temporary pain or temporary increases in existing pain prompted during the TMD clinical examination or PPT.

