2.3 Potential Risks and Benefits

2.3.1 Potential Risks

Use of Erenumab: Erenumab is a fully human monoclonal antibody that inhibits CGRP receptor and is FDA approved for the preventive treatment of migraine in adults. As of 16 May 2020, approximately 6,550 people have received erenumab in research studies. Since it was first approved for sale on 17 May 2018, approximately 423,800 people have been prescribed erenumab (Aimovig®) for treatment as of 16 May 2020.

The safety profile of erenumab has been favorable in clinical trials and in the post-marketing setting. A limited number of adverse drug reactions (injection site reactions, constipation, muscle spasm, and pruritus) have been identified at low frequencies (< 5%) in clinical trials. In the long-term use of erenumab, the safety profile remained consistent through 5 years of open-label treatment. In post-marketing settings, hypersensitivity reactions (including rash, angioedema and anaphylactoid reactions) and constipation with serious complications have been reported. In addition, oral sores (eg, stomatitis, mouth ulceration, oral mucosal blistering), alopecia and rash (eg, rash papular, exfoliative rash, rash erythematous, urticaria, blister) have been observed in post-marketing surveillance

Serious constipation has been reported in patients prescribed erenumab. In some cases, hospitalization or surgery was required. Constipation and the use of medications that decrease gastric motility are in our exclusion criteria, however if a new onset of constipation occurs, the participant will be withdrawn of the study and will be referred to an appropriate practitioner for continued care (see section 9.2).

Hypertension or worsening of high blood pressure can happen after receiving Erenumab. Hypertension is in our exclusion criteria, however if a new onset of hypertension occurs, the participant will be withdrawn of the study and will be the participant will be referred to an appropriate practitioner for continued care (see section 9.2)

After taking erenumab, antibodies against erenumab may be produced; this has been observed in clinical studies. No side effects associated with these antibodies were observed.

Side effects of the use of erenumab in combination with other drugs are unknown at this time.

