9 ASSESSMENT OF SAFETY

9.1 Specification of Safety Parameters

This study involves the use of Erenumab, a fully human monoclonal antibody that is a CGRP receptor antagonist FDA approved for the prevention of migraine in adults

The participants of this study will be closely monitored and follow up in their clinic visits and between visits with telephone calls. As part of the study outcomes, the study staff will record information regarding AEs. Overall health parameters will be captured on case report forms. These will be completed at every visit and data will be compiled for review by the IRB.

The description of potential risks is described in 2.3 and 6.3. The most common side effects of the use of Erenumab are:

- Injection site reactions: which may include tenderness, pain, redness, itching, bruising, firmness, or hypersensitivity
- Constipation
- Muscle spasms/cramps
- Itching (pruritus)

Allergic reactions can happen within hours to days after using erenumab. Therefore, after the injection is administered, the participant will wait in the room for 20 minutes and the evening of the treatment visit, the participant will receive a follow up phone call and the information will be recorded.

If the participant reports a hypersensitivity reaction (rash, angioedema, anaphylaxis), new onset constipation or new onset of hypertension or any of the reactions described above, if there is worsening of TMD signs and symptoms during the 18 weeks of participation or if the participant decides against using Erenumab, he/she will be discontinued from the study (See 2.3.1 and 5.5.2).

The following expected events will not be considered reportable AEs:

- Temporary injection site reactions such as pain, erythema, pruritus after the injection of Erenumab
- Minor bleeding or bruising resulting from the blood draw
- Temporary pain or temporary increases in existing pain prompted during the TMD clinical examination or PPT.

9.1.1 *Unanticipated Problems*

The Office for Human Research Protections (OHRP) considers unanticipated problems involving risks to subjects or others to include, in general, any incident, experience, or outcome that meets **all** of the following criteria:

- Unexpected in terms of nature, severity, or frequency given (a) the research procedures that are described in the protocol-related documents, such as the IRB-approved research protocol and informed consent document; and (b) the characteristics of the subject population being studied;

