9.3.2 Expectedness of SAEs

AMGEN and the Study PI will be responsible for determining whether an AE/SAE is expected or unexpected.

The most common adverse reactions (incidence $\geq 3\%$ and more often than placebo) in the migraine studies were injection site reactions and constipation. Common side effects that may affect between 1 and 10 people in every 100:

- Injection site reactions: which may include tenderness, pain, redness, itching, bruising, firmness, or hypersensitivity
- Constipation
- Muscle spasms/cramps
- Itching (pruritus)

Since erenumab was approved in May 2018, the following events have been reported in patient's exposed to erenumab in the post-marketing setting:

- 1) Severe allergic reactions such as rash, swelling and difficulty breathing, or swallowing.
- 2) Mouth/lip sores (e.g., stomatitis, mouth ulcerations, and oral mucosal blistering)
- 3) Skin and subcutaneous tissue disorders
 - o Alopecia (loss of hair)
 - o Rash (e.g., papular rash [small raised red rash], exfoliative rash [redness and/or peeling of skin], erythematous rash [red rash], urticaria [hives], and blisters)
- 4) Constipation and the use of medications that decrease gastric motility are in our exclusion criteria, however if a new onset of constipation occurs, the participant will be withdrawn of the study and will be referred to an appropriate practitioner for continued care (see section 9.2).
- 5) Hypertension or worsening of high blood pressure can happen after receiving Erenumab. Hypertension is in our exclusion criteria, however if a new onset of hypertension occurs, the participant will be withdrawn of the study and will be referred to an appropriate practitioner for continued care (see section 9.2)

An adverse event (AE) will be considered unexpected if the nature, severity, or frequency of the event is not consistent with the risk information previously described for the intervention, protocol, investigator's brochure and/or informed consent document.

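### The discontinuation rule in 6.3 (less clearly 9.1) has no severity limit, so read literally one mild, temporary injection-site reaction forces a participant out of the study

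*Combined protocol and SAP*

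**What the plan says.** Section 6.3 opens its safety text with this sentence: "A limited number of adverse drug reactions (injection site reactions, constipation, muscle spasm, and pruritus) have been identified at low frequencies (< 5"; the parenthesis closes with a percent sign, so the stated frequency is under 5%. It goes on to post-marketing events (hypersensitivity, serious constipation, oral sores, alopecia, rash) and to hypertension. It then says that a participant who reports a hypersensitivity reaction, "new onset constipation or new onset of hypertension or any of the reactions described above", is to be discontinued from the study. The instruction is mandatory and carries no limit of grade, duration or seriousness. Worsening TMD and the participant's own decision are further triggers in the same sentence.

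A short list follows directly, introduced by "The following expected events will not be considered reportable AEs". Section 9.1 carries the same discontinuation sentence and the same list, whose first item is "Temporary injection site reactions such as pain, erythema, pruritus after the injection of Erenumab".

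Three other sections deal with withdrawal:

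- 2.3.1, to which the rule refers, ties it to constipation ("however if a new onset of constipation occurs, the participant will be withdrawn of the study"), to hypertension, and to pregnancy, breastfeeding or fathering a child.
- 9.3.2 ties it to new constipation and new hypertension. It also says that the most common reactions (incidence at least 3% "and more often than placebo) in the migraine studies were injection site reactions and constipation").
- 5.5.1 is permissive. Investigators may withdraw a participant for an adverse event "such that continued participation in the study would not be in the best interest of the participant", and the list ends with a general investigator-discretion item.

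On consequences, 5.5.2 says: "Participants who are withdrawn voluntarily or by the investigator will be discontinued from the study". Those withdrawn after randomization are not replaced.

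**The concern.** Hypersensitivity, constipation and hypertension are already named in the sentence, so the catch-all at its end must add something. In 6.3 the most direct candidates are the other items that the section itself calls adverse drug reactions: injection-site reactions, muscle spasm and pruritus. Followed as written, a day of redness at the injection site ends participation, although the next lines treat that event as too minor to report. The exemption in those lines covers reporting only; it does not lift the discontinuation rule.

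What is at stake is outcome data. Leaving the study means leaving the diary as well as the drug. Under 3.2.1 a monthly mean is calculated only with at least 80% diary compliance, and 12.4 names an intention-to-treat analysis without saying how missing months are handled. Because 9.3.2 reports these reactions as more frequent than on placebo, exits under this rule would tend to fall more on the erenumab arm.

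**Working it through.** **The wording in 6.3 and 9.1.** In 6.3, injection-site reactions come first in the list and are called reactions, so the back-reference reaches them directly. In 9.1 the link is weaker: the list above the rule is headed as side effects, and the nearest paragraph concerns allergic reactions. A narrower reading is easier there.

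**The other sections.** For a mild, temporary injection-site reaction:

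| Section | What it implies |
|---|---|
| 6.3 rule, literal | mandatory exit |
| 9.1 rule | mandatory exit, or allergic-type reactions only; unclear |
| 6.3 and 9.1, list after the rule | expected and not reportable; silent on exit |
| 2.3.1, 9.3.2 | silent on exit |
| 5.5.1 | exit allowed, not required |

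**Scale.** The plan gives no figure for this point, so there is none to reproduce. Inputs: 30 patients on erenumab (5.4.1); incidence of at least 3% (9.3.2) and under 5% (6.3); a broader statement of 1 to 10 per 100 for the common effects (9.3.2); drop-out allowance of 15% (12.2). Assumptions: the 6.3 ceiling applies to injection-site reactions taken alone, migraine-trial rates carry over to TMD, patients are independent, and every case is withdrawn.

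Expected cases = 30 × p. Chance of at least one = 1 − (1 − p)^30. Allowance per arm = 0.15 × 30 = 4.5.

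| p | Expected cases | Chance of at least one | Share of 4.5 |
|---|---|---|---|
| 1% | 0.3 | 26% | 0.3/4.5 = 7% |
| 3% | 0.9 | 60% | 0.9/4.5 = 20% |
| 5% (upper bound, not reached) | 1.5 | 79% | 1.5/4.5 = 33% |
| 10% | 3.0 | 96% | 3.0/4.5 = 67% |

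Muscle spasm and pruritus would add to the literal count; no separate rates are given for them.

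**Imbalance between arms.** The expected excess on erenumab is 30 × (p_erenumab − p_placebo). The plan gives the direction but no value for p_placebo. The excess is below the counts above as soon as any such reactions occur on placebo, and its size cannot be computed.

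**Data lost per case.** Eighty percent of a 28-day cycle is 0.80 × 28 = 22.4 diary days. A participant who leaves within days of the first injection cannot reach that, and so has no on-treatment monthly mean.

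**The case against.** The best defence is that no sensible clinician would apply the rule this way. The following lines call temporary injection-site reactions expected, 9.1 leans towards allergic reactions, and 2.3.1, to which the rule refers, names no such withdrawal. That is persuasive about intent, and the literal result probably was not meant. It does not change the instruction in 6.3, which is mandatory and unqualified.

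A reader might infer that the protocol contradicts itself, with 2.3.1, 9.3.2 and 5.5.1 giving a different answer from 6.3. The documents do not support that. Sections 2.3.1 and 9.3.2 are not exhaustive trigger lists: they attach no withdrawal to hypersensitivity either, which 6.3 plainly requires. Section 5.5.1 is permissive and ends in open discretion, so a stricter rule in 6.3 can stand beside it. These sections are silent or flexible; they do not conflict with the rule.

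A reader might also infer that these reactions will go unrecorded, because 9.2 speaks of recording reportable events. That is speculative. Section 8.1, section 9.1 and the visit lists direct staff to record adverse events; reportable may refer to external reporting only; and parts of 9.4 are blacked out.

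Finally, the numbers are small, they sit inside the drop-out allowance, and the disposition form in 5.5.2 makes the reason for each exit traceable. Constipation, which 9.3.2 places in the same more-often-than-placebo statement, stays a mandatory trigger in any case. All of this stands, and it keeps the point minor.

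**Conclusion.** The point holds as a minor drafting fault. As written, 6.3 forces study exit for a mild, temporary injection-site reaction, and by the same words for mild muscle spasm or pruritus; 9.1 does so less clearly. No other section requires that outcome and none rules it out.

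The size is about 0.9 to under 1.5 of 30 erenumab patients at 3% to under 5%, or 0.3 to 3.0 over the 1% to 10% range. These are gross upper-scenario counts for injection-site reactions: they need migraine-trial rates to apply in TMD and every case to be withdrawn. They should not be read as a difference between arms or as a measure of bias; the placebo rate needed for either is not in the documents.

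**What to change.** In 6.3 and 9.1:

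- Keep mandatory discontinuation for a hypersensitivity reaction, new-onset constipation and new-onset hypertension. Leave the triggers for worsening TMD and participant decision as they are.
- Add that mild, temporary injection-site reactions after either study injection are not a reason to discontinue. The current exemption names erenumab alone, which blinded staff cannot apply by arm.
- Replace the catch-all with investigator judgment under 5.5.1 for other listed reactions, such as mild pruritus or muscle spasm. State expressly whether oral sores and alopecia move to judgment or remain automatic, so that no safety trigger is relaxed by accident.

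No change to 9.2 is needed for this point. The cost is a few words in two sections, with no new procedure. The small downside is that withdrawal for the reactions moved to judgment is no longer automatic. The gain is limited too: treatment-linked exits for constipation remain.
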